#### **5.4 Data Monitoring Committee (DMC)DMC General Information**

A Data Monitoring Committee (DMC) will oversee the performance and safety conduct of this study. The DMC will consist of at least three members (two MDs and one statistician as voting members) who will receive confidential reports on a periodic basis. The DMC will be responsible for decisions regarding possible termination of the study for either futility or safety reasons.

A detailed DMC Charter will be produced separately by the DMC membership. It is anticipated that any reviews of study data will be performed in a blinded manner, looking at pooled data (all treatment groups combined into one group) to assess mission-critical parameters such as overall recruitment and event rates. Of course, patient safety issues take precedence over bias-protection and control of type I error, and so the DMC will have the privilege of breaking the blind on a need-to-know basis if safety issues of concern arise in order to consider risk-benefit issues. Details concerning DMC responsibilities and duties may be submitted as a stand-alone document to the FDA and EMA, including items such as specification of early termination rules and other matters as the DMC deems to be important and relevant to the ethical conduct of this study.

CPP will inform the DMC that there will be two study evaluations for the DMC to consider during the trial, one interim look for sample size reassessment and one look for efficacy and futility.

The method for reassessment of sample size is based upon the FDA Guidance, *Adaptive Design Clinical Trials for Drugs and Biologics* (February 2010). There will be no hypothesis testing. The DMC will assess the observed trial event rate based on pooled data only. They will make a recommendation to the sponsor on whether the pooled event rate is sufficient to preserve the integrity of the trial, and if not, to recommend a revised sample size. For this assessment the study statistician will, if possible, estimate the overall observed event rate and 90% confidence interval. This assessment will be performed using data from a single time point, when enrollment is approximately 95% complete. If this type of assessment is not possible, then an assessment will be performed taking into consideration the total number of subjects randomized, total number of events, total number of dropouts, and cumulative study safety data.

##### **5.4.2 Prespecified Interim Efficacy and Futility Analysis**

A pre-specified interim efficacy and futility analysis will be conducted as described below. The assessment will be performed after a total of 45 primary endpoints have occurred, which represents 50% of expected maximum trial information, or as soon thereafter as possible. After reviewing the analysis results in a closed session, the DMC will provide recommendations regarding possible termination of the study for either futility, efficacy, or safety reasons, to the Sponsor Steering Committee.

The analysis will be performed for each of the two treatment comparisons contained in the

primary objective:

1. CPP-1X placebo + sulindac active vs. CPP-1X active + sulindac active,  
and
2. CPP-1X active + sulindac placebo vs. CPP-1X active + sulindac active.

As stated above in Section 3.2, the combination of CPP-1X active + sulindac active is specified as the reference treatment group because it is common to both comparisons and formulating the hypothesis tests in this manner will allow a positive rather than a negative Z-score for the test statistic to be interpreted as supportive of this purpose.

The efficacy analysis will use a modified Haybittle-Peto stopping rule based on the stratified log-rank Z-score. If that Z-score equals or exceeds 3.2905 in absolute value, for either two-arm comparison, the difference between treatment arms would be declared statistically significant at the two-tailed 0.001 level of significance. In that case it may be reasonable for the DMC to initiate a conversation about stopping the trial on ethical grounds. Assuming this is not the case and the trial continues to its planned end, the Z-score criterion for declaring significance at the 5% level at the end of the trial will be increased in magnitude to plus or minus 1.962 in order to preserve the overall type I error rate for the trial at 0.05.

For the futility analysis, the DMC will be provided with the numerical value of the stratified log-rank Z-score. The futility analysis uses a one-sided futility stopping criterion of  $Z = -0.50$ . That is, if the Z-score is less than or equal to  $-0.50$ , an investigation will be initiated to consider stopping the trial for futility or discontinuing one of the single-agent treatment arms. The futility stopping criterion of  $Z = -0.50$  is consistent with a conditional power of less than 20%. That is, assuming between 44 and 60 FAP-related events have occurred by trial end in either of the two-arm comparisons (where between 52 and 55 are expected), if the log-rank critical ratio Z-score were equal to  $-0.5$  (or less) when one-half the expected total number of events had been observed (namely, 45 across all three arms), then under the design alternative hazard ratio of 2.3569, there would be no more than a 20% chance of declaring a significant benefit of the combination therapy compared to the single agent therapy if the trial were to continue to the planned end. In that case, it would be reasonable for the DMC to consider stopping or altering the trial on grounds of futility. The DMC will also be provided with the conditional power of the observed Z-score for each two-arm comparison.

The details of the efficacy and futility analysis are provided in Table 5.1 below which presents a schematic diagram of the procedure. Also Table 5.2 provides more precise conditional power values corresponding to the futility criterion  $Z = -0.50$  as a function of the total number of events in either two-arm comparison. See Section 7.4 below for further details of the conditional power calculation.

Any numerical values generated from the futility analysis (such as Z-score, conditional power, etc.) must be treated as confidential by the DMC and Independent Statistician at the CRO. If the DMC recommendation is to continue the study as planned, such numerical values will not be forwarded or conveyed in any manner to the Steering Committee, sponsor, or any other parties.

**Table 5.1 Interim Futility Analysis Details**

Estimated Look Time Point	Description
When 45 primary endpoints have occurred, corresponding to when 50% of maximum trial information has been amassed	
Efficacy criterion <math>Z = 1.962</math> at terminal analysis.
 
Futility criterion of <math>Z = -0.50</math> or less at interim analysis.
 
Type I error for exiting the upper efficacy boundary at or before terminal analysis = 0.024952.*
 
Type I error for exiting the lower efficacy boundary at or before terminal analysis = 0.001928.*
 
Total Type I error for end of study comparison = 0.026936.*
 
Assuming 52 events at trial end in either two-arm comparison, power = 0.8705.
 
Assuming 55 events at trial end in either two-arm comparison, power = 0.8881.

\*Assume one interim analysis at  $\frac{1}{2}$  information time with upper efficacy boundary at  $B_e = 3.2905$ , lower efficacy boundary at  $-B_e$ , and one-sided futility boundary  $B_f = -0.50$ . Assume upper efficacy terminal criterion  $C = 1.9602$  and lower efficacy terminal criterion  $-C$ . Then the probability of exiting the upper efficacy boundary at either interim or terminal analysis under the null hypothesis is given by

[figure not shown]
$$\Phi(-B_e) + \int_{B_f}^{B_e} \Phi(z - C\sqrt{2})\varphi(z)dz$$

and the probability of exiting the lower efficacy boundary at either interim or terminal analysis under the null hypothesis is given by

$$\Phi(-B_e) + \int_{B_f}^{B_e} \Phi(-z - C\sqrt{2})\varphi(z)dz,$$

where  $\varphi(z)$  is the standard normal probability density function and  $\Phi(z)$  is the standard normal cumulative distribution function.

**Figure 5.1 Schematic Diagram for Efficacy, Futility, and Terminal Analyses**

**Table 5.2 Conditional Power at the Futility Boundary as a Function of Number of FAP Events at the Time of Futility Analysis, Using Futility Criterion  $Z = -0.5$**

Total FAP events in either two-arm comparison at time of futility analysis	Assumed number of FAP-related events in either two-arm comparison at trial conclusion	Conditional power
30	60	0.177
29	58	0.167
28	56	0.157
27	54	0.148
26	52	0.138
25	50	0.129
24	48	0.120
23	46	0.111
22	44	0.103

## 5.5 Statistical Methods

### 5.5.1 Demographic and Baseline Characteristics

Patients in the three populations (see Section 4.) will be summarized for demographic and baseline characteristics in a descriptive fashion. Namely, categorical and continuous-valued data will be displayed using standard summary statistics (e.g., frequency tables, n, means, medians,

standard deviations, and ranges). Data will be presented per group and overall.

Demographic features summarized will include age, gender, race, institution at which each patient registered, and country, among other features. Baseline characteristics will include laboratory values and disease-related characteristics, as well as any other relevant values. Categorical data will be compared among groups using chi-squared methods, while continuous-valued data will be compared using standard nonparametric methods (e.g., the Kruskal-Wallis test)[5]. Significance will be defined at the 0.05 level, unless otherwise noted. Thus p-values less than or equal to 0.05 will be declared significant.

### **5.5.2 Patient Disposition and Treatment Summaries**

Subjects will be assigned for analysis to the treatment group to which they were randomized, regardless of whether the patients received any treatment.

Patient disposition and treatment will be summarized for the ITT and safety populations defined previously (see Section 4.2). Patient disposition will be consistent with the CONSORT criteria[6], and will include per treatment group enumeration of all patients randomized, the number deemed ineligible, the number of FAP-related events, and the number of study drop outs. These will be further described in subgroups such as drop outs due to adverse events, serious adverse events, administrative withdrawals for non-compliance for more than 90 days from randomization to month 36 or more than 105 days from randomization to month 42 or more than 120 days from randomization to month 48, withdrawals of consent for continued follow-up, withdrawals for other reasons, and the number lost to follow-up. Additional summaries will include reasons for patients discontinuing treatment and/or modifying treatment dosages. A listing of screened and ineligible patients along with the reason for each also will be summarized.

### **5.5.3 Analytic Methods for Time-to-Event Data**

The analytic method for the primary analysis will be a time-to-event analysis using the stratified log-rank test, as previously described. The stratified Cox proportional hazards regression models will be used for secondary assessments[7]. Graphical analyses (log-minus-log plots) will be used to check the assumption of constant hazard ratios. See Section 7.3 below for further details of the calculation of the stratified log-rank statistic.

For the primary analysis, two stratified log-rank tests will be performed with treatment coded as a binary value (i.e., 0 or 1). Time to event curves will be displayed using the method of Kaplan and Meier[8]. Additional analyses involving the overall 3-treatment group comparison, and use of additional study populations (see Section 4.) for the two pairwise treatment comparisons, will be performed as supplemental analyses.

If an FAP-related event occurs, that patient will be said to have an observed or uncensored event and will be considered a treatment failure. If a subject withdraws, that subject will be treated as a censored observation as of the last recorded clinic visit (endoscopic disease assessment).

If a subject has not progressed or is not known to have died at the date of analysis cut-off, time to first FAP-related event will be censored at the date of the last adequate endoscopy procedures before the cut-off date. Similarly, if a subject discontinues study participation due to toxicity and begins receiving other therapy, the time to FAP event will be censored at the date of the last adequate endoscopy procedure.

If a subject has two or more missing assessments, time to first FAP-related event for the subject will be censored at the time of last adequate evaluation prior to the missing assessment.

If a subject has no baseline assessment, time to first FAP-related event for the subject will be censored at the date of randomization.

See Section 5.5.6 below for further details of handling missing data. Every effort will be made to minimize the occurrence of censoring and missing data.

Prior to the primary analysis, balance will be assessed between the three arms in terms of key potential confounders measured at the baseline visit. If any of these variables is found significantly out of balance across the three groups using a 2 degree of freedom test of homogeneity at the 0.01 level of significance, it will be incorporated into a sensitivity analysis using a stratified Cox model including that term in addition to the treatment arm. The primary result for the trial will be the unadjusted stratified log-rank test. The covariate-adjusted score test (adjusted stratified log-rank test) will serve only as a secondary analysis to aid in the interpretation of the primary result.

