#### **4.4. Primary Outcome**

The primary objective of this trial is to determine whether the combination of CPP-1X plus sulindac is superior to either treatment individually, in delaying the time from the date of randomization to the date of the first occurrence of any FAP-related event in the subject as a whole. This includes: 1) FAP related excisional intervention involving the colon, rectum, pouch, duodenum and/or 2) clinically important events which includes progression to more advanced duodenal polyposis (Stage 2, 3 or 4), cancer or death. Section 8.2.14 provides complete detail.

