### **8.2.14. Definition of FAP-Related Events or Serious and Unexpected Toxicity**

The time from the date of randomization to the date of the first occurrence of any FAP-related event at any disease site (colon/rectum/pouch, duodenum) will lead to discontinuation of the study treatment. Follow-up of the subject for FAP-related events will continue, per protocol, until the end of the 30 day post-treatment.

FAP-related primary events by disease site are as follows:

1. Pre-operative, intact colon:
  - a) Disease progression^ indicating need for colectomy with IRA or total proctocolectomy
2. Rectum or pouch events include one or more of the following:
  - a) Excisional intervention by surgical snare or trans-anal excision to remove any polyp  $\geq 10$  mm in size (per pathology report) and/or pathologic evidence of high grade dysplasia.\*
  - b) Disease progression^ indicating need for proctectomy
  - c) Disease progression^ indicating need for pouch resection
  - d) Development of cancer in rectum or pouch
  - e) Death
3. Duodenal disease includes the following:
  - a) Progression in Spigelman Stage to more advanced stage (Stage 2, 3 or 4), refer to Appendix A
  - b) Disease progression indicating need for excisional intervention (sub-mucosal resection, trans-duodenal excision, ampullectomy, duodenectomy, Whipple procedure)
  - c) Development of cancer
  - d) Death

Note, excisional intervention may include open surgery, trans-anal surgery or endoscopic excisions/snare but does not include cautery ablations or hot biopsy.

\*For those subjects stratified to the duodenal group, all concurrent rectal pouch polyps  $> 5$  mm must have been removed at baseline for this event to apply.

^Disease progression is based on endoscopic evaluations compared to baseline demonstrating a clinically significant increase in number and/or size of polyps (~25% increase in disease burden), presence of a large sessile or ulcerated adenoma not amenable to removal, high grade dysplasia in any adenoma, or in-situ or invasive cancer.

Discontinuation from study treatment due to a potential treatment related serious adverse event may include the following:

- Gastrointestinal hemorrhage,  $\geq$  grade 3
- Tinnitus  $\geq$  grade 2, or clinical hearing impairment  $\geq$  grade 3

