### **8.3.2. Protocol Treatment Withdrawal (Off-Study Treatment)**

Participants will be withdrawn from protocol treatment under the following circumstances:

1. Evidence of an FAP-related event as defined in Section 8.2.14.
2. Clinical reduction in hearing acumen requiring use of a hearing aid.
3. Grade  $\geq 3$  cardiac ischemia/infarction or cerebrovascular ischemia, whether related to study drug or not.
4. Pregnancy while on treatment, see Section 11.8.
5. Intercurrent illness which would, in the judgment of the treating physician, affect assessments of clinical status to a significant degree and/or require discontinuation of drugs. Participants will not discontinue study drugs for other medical events which are not considered to be treatment related. This determination will be made by the treating physician.
6. Cumulative delay of study intervention for any reason as follow:
  - > 90 days from randomization to month 36
  - > 105 days from randomization to month 42 or
  - > 120 days from randomization to month 48

The first day of study treatment initiation is the randomization date regardless of study visit and/or procedure delays.

7. Completion of treatment intervention.
8. At the request of the Sponsor in situations such as protocol violations or concerns about the subject's safety.
9. The subject is lost to follow-up.
10. The subject may withdraw from the study-treatment at any time for any reason.
11. Subject death.

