**Table 3.2 Overall Event Free Proportions After Two Years of Follow-up\***

Treatment	S(t)	t (months)	Median Time to Event (months)
Combination	0.6	24	32.566
Single Agent	0.3	24	13.817

\*These proportions are assumed for design purposes only. The median times to event are based on the assumption of an exponential time-to-event function S(t) in each group.

At least 150 eligible patients will be enrolled in this study, with at least 50 per treatment group. Patients will be randomized to one of three treatment groups within the prognostic strata defined above in equal proportions (i.e., 1:1:1 randomization): 1) CPP-1X plus sulindac, 2) CPP-1X placebo plus sulindac, 3) CPP-1X plus sulindac placebo. The study is double blinded, so neither patients nor Investigator nor Sponsor will be aware of treatment assignment.

The grading of adverse events will be based on the current version of the NCI Common Terminology Criteria for Adverse Events (CTCAE Version 4.03).

Refer to the CPP FAP-310 protocol for the details of the treatment and study schedule, and description of study procedures and tests.

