### 3.2.4 Other Secondary Outcomes

To explore how study treatment group relates to other efficacy outcomes, genotype, phenotype, disease locations and endoscopic findings, additional analyses are planned. These analyses will be performed in the ITT group, the Per Protocol Group, and other defined subgroups (see Section 4 Populations for Analysis) wherever possible and will all be clearly noted as such.

The UGIOI and LGIOI outcomes will be tabulated and summarized using the month 6 visit scores, alone. Similarly, the UGIOI and LGIOI outcomes will tabulated and summarized across all study visits.

As both part of the primary analysis, and further explored in these additional analyses, median time to event for each treatment group will be determined. This will be explored for each of the study populations (i.e. ITT, per protocol, and others), study disease stratum groups, and in the Disease Site subgroups (see below).

Pharmacokinetic data (plasma concentrations measured at patient visits) will be used to estimate population pharmacokinetic parameters for the CPP-1X (eflornithine), sulindac, and CPP-1X (eflornithine) + sulindac treatment groups (i.e. for each analyte for those patients on combination treatment).

The subcategories of FAP events will be explored by disease stratum groups, and by Disease Site subgroups (see below). The subcategories of FAP events include:

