8	Development of cancer in duodenum	Does not apply to subjects without duodenum (determined by abdominal surgical procedure of duodenectomy, duodenohemipancreotomy, or Whipple procedure (field name SXPROC) and screening/baseline upper GI endoscopy not done (field name UGIND, Boolean data type)
9	Spigelman stage (no progression)	Does not apply to subjects without duodenum (determined by abdominal surgical procedure of duodenectomy, duodenohemipancreotomy, or Whipple procedure (field name SXPROC) and

No	Group	Description
		screening/baseline upper GI endoscopy not done (field name UGIND, Boolean data type)
10	>= 10 mm polyp in rectum pouch	Does not apply to subjects with FAP surgical status of colectomy with ileostomy (field name: DIAGSXST, code 4) or subjects with FAP surgical status of precolectomy (field name: DIAGSXST, code 1). For all remaining subjects, all >5 mm polyps must have been removed at baseline.
11	High grade dysplasia (rectum-pouch)	Does not apply to subjects with FAP surgical status of colectomy with ileostomy (field name: DIAGSXST, code 4)

These subcategories will be analyzed within the assigned disease strata (i.e. assigned at time of randomization). Separately, they will be analyzed by Disease Site, according to the concept of “the patient as a whole” meaning that *all known disease sites will be considered* because patients more often than not have more than one diseased organ system. For example, a patient randomized to treatment in the Duodenal Polyposis stratum who is also known to have colonic polyps will appear in the analyses for both Disease Site subgroups (Duodenal and Colonic). The total number of patients in the Duodenal Disease Site subgroup will include, for example, all patients randomized in the Duodenal Polyposis stratum + all other patients with known duodenal disease (irrespective of whether they have rectal/pouch disease). A similar approach will be taken for the Rectum/Pouch Polyposis group and Pre-colectomy strata.

The presence or absence of ODC polymorphisms, including the single nucleotide polymorphisms (SNPs) rs2302615 and rs2302616 and their relation to treatment group and outcome will be tested with the likelihood ratio test.

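### The rules on death as a primary event conflict, and the censoring sentence as worded censors a death without progression

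*SAP*

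**What the plan says.** **Protocol.** Section 4.4 defines the primary outcome for the subject as a whole. Besides excisional interventions it includes "clinically important events which includes progression to more advanced duodenal polyposis (Stage 2, 3 or 4), cancer or death", and it points to 8.2.14 for full detail. Section 8.2.14 opens its list with "FAP-related primary events by disease site are as follows". Death appears there as item 2(e), rectum or pouch, and item 3(d), duodenum. The intact colon has the single item 1(a), progression indicating a need for colectomy. Section 8.3.2 gives "Subject death" as item 11 among the reasons for leaving protocol treatment, separate from item 1, an FAP-related event.

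**SAP.** Section 5.5.3 begins with a general rule: "If an FAP-related event occurs, that patient will be said to have an observed or uncensored event". It does not say which occurrences are FAP-related events. The next paragraph censors at the last adequate endoscopy before the cut-off: "If a subject has not progressed or is not known to have died at the date of analysis cut-off". Protocol 12.1 carries the same sentence. The SAP's only itemised list of event types is Table 3.3, introduced in 3.2.4 by "The subcategories of FAP events include"; none of its eleven rows is death. The general pointer to the protocol in SAP 3.1 reads "Refer to the CPP FAP-310 protocol for the details of the treatment and study schedule, and description of study procedures and tests". It does not expressly cover the event definition.

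**The concern.** Whether a death is an event or a censored time should follow unambiguously from the written rule. Here 4.4 says it is an event, 8.2.14 says so for two of three disease sites, the SAP does not say, and the censoring sentence read literally says it is censored. A programmer working from the SAP alone would find no statement that death counts and one sentence that, as worded, censors it.

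If deaths occur, someone must settle this at derivation. Settled after unblinding, it becomes a choice about the primary endpoint made with results in view. Censoring a death also treats it as uninformative about the outcome, although 4.4 makes it part of the outcome.

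**Working it through.** **1. The censoring sentence as a logical rule.** Let P mean progressed and D mean known to have died. As written, the subject is censored if (not P) or (not D).

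| Progressed | Died | Written rule (*or*) | With *and* | Protocol 4.4 |
|---|---|---|---|---|
| No | No | censored | censored | no event |
| No | Yes | **censored** | not censored | event |
| Yes | No | **censored** | not censored | event |
| Yes | Yes | not censored | not censored | event |

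The written rule disagrees with 4.4 in the second and third rows. The *and* version agrees in all four. The third row also contradicts the opening rule of SAP 5.5.3, so the conjunction must be a drafting error.

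**2. Event definitions side by side.** Items 1(a), 2(a) to 2(d) and 3(a) to 3(c) of Protocol 8.2.14 correspond to rows 1 to 8 of SAP Table 3.3. Items 2(e) and 3(d), both death, have no row. Row 9 is a no-progression category, and rows 10 and 11 take up the two parts of row 2 separately. Within 8.2.14, a pre-colectomy subject with no other listed site has no death item, although 4.4 makes no such exception.

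**3. Size.** Inputs from the SAP: design hazard ratio log(0.60)/log(0.30) = 0.4243, absolute log hazard ratio 0.85736 (5.3 and 7.4); 49 events per comparison for 85% power (5.3); power 0.8705 at 52 events (Table 5.1); final critical value 1.962 (5.4.2). The number of deaths is not given.

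The plan's own figures reproduce with the Schoenfeld formula:

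- Events = 4 × (1.960 + 1.036)² / 0.85736² = 48.9, rounded up to 49.
- Power at 52 events = Φ(√(52/4) × 0.85736 − 1.962) = Φ(1.129) = 0.8706, against 0.8705 stated. With 1.960 it is 0.8710.

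Suppose *d* deaths per comparison are censored instead of counted and deaths carry the same hazard ratio as other events (both are assumptions). Power at the design hazard ratio, with critical value 1.960:

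| d | from 52 events | from 49 events |
|---|---|---|
| 0 | 0.871 | 0.851 |
| 1 | 0.865 | 0.844 |
| 2 | 0.858 | 0.836 |
| 5 | 0.836 | 0.811 |

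For direction, a positive Z favours the combination (SAP 7.3). With similar numbers at risk in the two arms, one death moves the log-rank numerator by about 0.5. With 52 events its standard error is about √(52/4) = 3.61. To first order, one censored death therefore shifts Z by 0.5/3.61 = 0.14: upward if the death was in the combination arm, downward if it was in the single-agent arm. The expected Z at the design hazard ratio is 0.85736 × 3.61 = 3.09.

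**The case against.** The strongest reply is that nobody could implement the literal sentence. It would censor every living subject who progressed and so remove most primary events. The paragraph before it makes every FAP-related event uncensored, and a censoring sentence has reason to mention death only if death is an endpoint. The SAP analyses the protocol's endpoint and need not repeat its components. This stands as evidence of intent: death was very probably meant to count. It does not make the written rule correct, and it does not fill the intact-colon gap in 8.2.14.

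That gap is narrow. Events at any site count for the subject as a whole, so a pre-colectomy subject who also has duodenal disease is covered by item 3(d). It remains a mismatch with 4.4.

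A reader might infer that Table 3.3 defines the primary endpoint, so that its missing row removes deaths from the primary test. The documents do not support this. The table sits under other secondary outcomes, is titled as disease site subgroups, serves an exploratory breakdown and includes a row that is not an event. Nothing says the primary endpoint is derived from it. The missing row only leaves that breakdown incomplete.

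A reader might also infer from the sulindac warnings in Protocol 2.7.3 that censoring deaths would favour the combination. In the first, gatekeeping comparison both arms take sulindac 150 mg, so the warnings give no reason to expect more deaths on the combination. They could bear only on the comparison with CPP-1X alone. Protocol 6.2 excludes listed cardiovascular risk factors, and Protocol 3.2 reports that the data monitoring committee had identified no safety issues as of June 2017.

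Item 11 of Protocol 8.3.2 might be read as a second route to censoring, because SAP 5.5.3 censors subjects who withdraw. But 8.3.2 concerns leaving treatment and does not say that a death ends follow-up as a censored time.

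**Conclusion.** The point holds as an internal inconsistency in the primary endpoint rules. The censoring sentence in SAP 5.5.3 and Protocol 12.1 is wrong as written, 8.2.14 does not match 4.4 for the intact colon, and the SAP does not state that death is an event. The documents do not show a decision to censor deaths.

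The numerical effect is nil with no deaths and small with one or two: at the design hazard ratio, a power loss of 0.006 to 0.013 from 52 events, and a shift in Z of about 0.14 per death in either direction. These figures rest on an assumed number of deaths, a common hazard ratio for deaths and other events, and similar numbers at risk in the two arms.

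A reader might infer that a borderline result would be tipped towards the combination. That requires the deaths to fall in the combination arm and the result to lie close to 1.962; the documents support neither. The reason to correct the text is that the rule is wrong and should be settled before unblinding. No sample-size or power figure in the plan changes.

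**What to change.** 1. In SAP 5.5.3 and Protocol 12.1, change the condition to *has not progressed and is not known to have died*.
2. In SAP 5.5.3, state that death from any cause is a primary event, dated at death, in every stratum. Say in the same place how a death after two or more missed assessments, or after withdrawal, is handled, because the existing censoring rules also touch those cases.
3. Reconcile Protocol 8.2.14 with 4.4 by listing death once for all disease sites, including the intact colon.
4. Add a death row to SAP Table 3.3, applying to all subjects, so that the exploratory breakdown covers every component.

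The cost is a few sentences in each document and one line in the endpoint derivation. No change to data collection or sample size is needed.
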